4.1. Overall Design

Study AACN is a multicenter, randomized, open-label, head-to-head, Phase 3 study of donanemab compared to aducanumab in participants with early symptomatic AD.

Participants who meet entry criteria will be randomized in a 1:1 ratio to 1 of the following treatment groups:

- donanemab: 700 mg IV Q4W for first 3 doses and then 1400 mg IV Q4W
- aducanumab: refer to PI/routine clinical practice

The maximum total duration of study participation for each participant, including screening and the post-treatment follow-up periods, is up to 127 weeks:

- Lead-In: any time prior to complete screening
- Complete Screening: up to 7 weeks
- Open-label study period: 76 weeks
- Follow-Up: up to 44 weeks

The maximum duration of treatment is 72 weeks.

Scheduled Reduction of Donanemab

Participants randomized to donanemab whose amyloid plaque reduction as measured by florbetapir F18 PET scans at Visit 8 (Week 24) or Visit 15 (Week 52) meets criteria will stop donanemab infusions but continue all other assessments for the remaining duration of the open-label period and short-term follow-up period. These dose reduction rules are defined by the sponsor.

Participants randomized to aducanumab will continue monthly infusions throughout the open-label period, regardless of amyloid plaque reduction on florbetapir F18 PET scans.

Change in amyloid burden (as assessed with florbetapir F18 PET by personnel blinded to treatment allocation) will be compared in donanemab and aducanumab-treated participants.

Participant randomization will be stratified by amyloid burden and ApoE ϵ 4 status (noncarrier/heterozygous/homozygous).

4.2. Scientific Rationale for Study Design

Study AACN is a Phase 3, open-label, head-to-head study to evaluate the superiority of donanemab to aducanumab in reaching amyloid plaque clearance in participants with early symptomatic AD.

Amyloid plaque is a known hallmark pathology of AD, and is hypothesized to contribute to the cognitive and functional decline in people with AD. Therefore, it is hypothesized that the removal of amyloid by donanemab may slow clinical progression.

The study includes a screening visit, which can last up to 49 days, at which participants are required to have florbetapir F18 PET imaging results in order to be randomized to donanemab or aducanumab. The duration of the open-label treatment period of the study is 76 weeks and

includes up to 72 weeks of treatment with primary endpoint measure at 6 months, to assess the superiority of donanemab versus aducanumab in reaching amyloid plaque clearance.

In addition to AE reporting, safety measures such as laboratory assessments, MRI assessments (ARIA and emergent radiological findings), serious hypersensitivity reactions, and assessments of suicidal ideation and behavior are included to facilitate a comprehensive safety evaluation.

4.3. Justification for Dose

Decreased participant burden with a Q4W dosing schedule compared with a Q2W dosing schedule and comparable safety (see IB), 1400 mg Q4W dosing was selected as the highest dose regimen for robust amyloid plaque lowering. Safety data from Study AACG showed that the 1400-mg dose of donanemab had an acceptable safety profile based on the ability to monitor and manage AEs and AEs of special interest including ARIA-E, ARIA-H and hypersensitivity reactions, and the overall frequency, severity, and seriousness of AEs at this dose level.

A titration schedule of 700 mg IV Q4W for the first 3 doses and then 1400 mg IV Q4W was chosen to decrease the risk of ARIA-E.

Participants randomized to the aducanumab arm will receive approved-label dosing for aducanumab.

4.4. End of Study Definition

The end of the study is defined as the date of the last visit of the last participant in the study.

A participant is considered to have completed the study if the participant has completed all periods of the study including the last visit or the last scheduled procedure shown in the SoA.

5. Study Population

Prospective approval of protocol deviations to recruitment and enrollment criteria, also known as protocol waivers or exemptions, is not permitted.

5.1. Inclusion Criteria

Participants are eligible to be included in the study only if all of the following criteria apply:

Age

1. Participant must be 50 to 85 years of age inclusive, at the time of signing the informed consent.

Type of Participant and Disease Characteristics

2. Gradual and progressive change in memory function reported by the participant or informant for ≥ 6 months.
3. Meet florbetapir F18 PET scan criteria.
4. A Clinical Dementia Rating (CDR)-Global Score of 0.5 or 1.
5. An MMSE score between 20 and 30 (inclusive).
6. Must consent to apolipoprotein E (ApoE) genotyping.
7. Have a study partner who will provide written informed consent to participate, is in frequent contact with the participant (defined as at least 10 hours per week), and will accompany the participant to study visits or be available by telephone at designated times.

A second study partner may serve as backup. The study partner(s) is/are required to accompany the participant for signing consent. One study partner is requested to be present on all days the C-SSRS is administered and must be present at screening for the completion of the CDR. Other visits must have a study partner available by telephone if not accompanying participant at a visit for the following assessments:

- AEs and concomitant medications
- Relevant portions of the C-SSRS

If a study partner must withdraw from study participation, a replacement may be allowed at the investigator's discretion. The replacement will need to sign a separate informed consent on the first visit that he or she accompanies the participant.

8. Have adequate literacy, vision, and hearing for neuropsychological testing in the opinion of the investigator at the time of screening.
9. Are reliable and willing to make themselves available for the duration of the study and are willing to follow study procedures.

Sex and Contraceptive/Barrier Requirements

10. Males and females will be eligible for this study.
 - a. Contraceptive use by men or women should be consistent with local regulations regarding the methods of contraception for those participating in clinical studies.

- b. Female participants.
 - a. Women not of childbearing potential (defined in Appendix 4, Section 10.4) may participate.

Informed Consent

11. Capable of giving signed informed consent as described in Appendix 1, which includes compliance with the requirements and restrictions listed in the ICF and in this protocol.

5.2. Exclusion Criteria

Participants are excluded from the study if any of the following criteria apply:

Medical Conditions

12. Significant neurological disease affecting the central nervous system (other than AD), that may affect cognition or ability to complete the study, including but not limited to, other dementias, serious infection of the brain, Parkinson's disease, multiple concussions, history of transient ischemic attack or stroke, or epilepsy or recurrent seizures (except febrile childhood seizures).
13. Current serious or unstable medical illnesses including cardiovascular, hepatic, renal, gastroenterologic, respiratory, endocrinologic, psychiatric (including actively suicidal or deemed at risk of suicide, or current alcohol or substance abuse), immunologic, infectious, or hematologic disease and other conditions that, in the investigator's opinion, could interfere with the analyses in this study; or has a life expectancy of approximately ≤ 24 months.
14. History of clinically significant multiple or severe drug allergies, or severe posttreatment hypersensitivity reactions (including but not limited to erythema multiforme major, linear immunoglobulin A dermatosis, toxic epidermal necrolysis, and/or exfoliative dermatitis).
15. History of bleeding disorder or use of medications with platelet anti-aggregant or anti-coagulant properties (unless aspirin at ≤ 325 mg daily).

Imaging, Electrocardiograms, Laboratory Tests, and Physical Examination

16. Have any clinically important abnormality at screening, as determined by the investigator, on physical or neurological examination, ECG, MRI, or clinical laboratory test results that could be detrimental to the participant, compromise study integrity, or show evidence of other etiologies for dementia.
17. Have any contraindications for MRI, including claustrophobia or the presence of contraindicated metal (ferromagnetic) implants/cardiac pacemaker.
18. Have a centrally read MRI demonstrating presence of ARIA-E, >4 cerebral microhemorrhages, more than 1 area of superficial siderosis, any macrohemorrhage or severe white matter disease at screening.
19. Contraindications to having a PET scan.
20. Sensitivity to florbetapir F18 or flortaucipir F18.
21. Poor venous access.

22. Present or planned exposure to ionizing radiation that, in combination with the planned administration of study PET ligands, would result in a cumulative exposure that exceeds local recommended exposure limits.
23. ALT $\geq 2.5X$ ULN of the performing laboratory, AST $\geq 2.5X$ ULN, TBL $\geq 1.5X$ ULN, or ALP $\geq 2X$ ULN at screening.

Note: Participants with TBL $\geq 1.5X$ ULN are not excluded if they meet all of the following criteria for Gilbert's syndrome:

- Bilirubin is predominately indirect (unconjugated) at screening (direct bilirubin within normal limits).
- Absence of liver disease.
- ALT, AST, and ALP $\leq 1X$ ULN at screening.
- Hemoglobin is not significantly decreased at screening.

Prior/Concomitant Therapy

24. Have known allergies to donanemab or aducanumab, related compounds, or any components of the formulation.
25. Have had prior or current treatment with donanemab or aducanumab.

Prior/Concurrent Clinical Study Experience

26. Prior or current participation in any active or passive immunotherapy study targeting A β , unless documentation of receipt of placebo.
27. Are currently enrolled in any other interventional clinical trial involving a study intervention or any other type of medical research judged not to be scientifically or medically compatible with this study.
28. Have participated, within the last 30 days, in any clinical trial involving a study intervention. Participation in observational studies may be permitted upon review of the observational study protocol and approval by the sponsor.

Other Exclusions

29. Are study personnel directly involved with the execution of this study, and/or their immediate families. Immediate family is defined as a spouse, parent, child, or sibling, whether biological or legally adopted.
30. Are Lilly employees or are employees of TPOs directly involved in the study which requires exclusion of their employees, or have study partners who are Lilly employees or are employees of TPOs involved in a study which requires exclusion of their employees.

5.3. Lifestyle Considerations

Participants should refrain from donating blood or blood products from the time of their screening visit until 6 months following the last dose of study intervention.

Participants should avoid excessive use of alcohol from the screening visit until the study ends. Excessive alcohol consumption is defined for men as consuming an average of more than 3 drinks per day, or more than 21 drinks per week. For women, excessive use of alcohol is defined as consuming an average of more than 2 drinks per day, or more than 14 drinks per week.

5.4. Screen Failures

A screen failure occurs when a participant who consents to participate in the clinical study is not subsequently enrolled in the study. A minimal set of screen failure information is required to ensure transparent reporting of screen failure participants to meet the Consolidated Standards of Reporting Trials (CONSORT) publishing requirements and to respond to queries from regulatory authorities. Minimal information includes demography, screen failure details, eligibility criteria, and any SAE.

Individuals who do not meet the criteria for participation in this study (screen failure) may not be rescreened.

5.5. Criteria for Temporarily Delaying Enrollment/Randomization/Administration of Study Intervention of a Participant

Not applicable.

6. Study Intervention(s) and Concomitant Therapy

Study intervention is defined as any investigational intervention(s), marketed product(s), placebo, or medical device(s) intended to be administered to/used by a study participant according to the study protocol.

6.1. Study Intervention(s) Administered

Intervention Name	donanemab	aducanumab
Dosage Level(s)	700 mg IV Q4W for first 3 doses and then 1400 mg IV Q4W ^a	refer to PI/routine clinical practice
Route of Administration	IV infusion	IV infusion
Use	experimental	active-comparator

Abbreviations: IV = intravenous; PET = positron emission tomography; PI = package insert; Q4W = once every 4 weeks.

^a Participants randomized to donanemab whose amyloid plaque reduction as measured by florbetapir F18 PET scans at Visit 8 (Week 24) or Visit 15 (Week 52) meets criteria will stop donanemab infusions but continue all other assessments for the remaining duration of the open-label period and short-term follow-up period. These dose reduction rules are defined by the sponsor.

Donanemab is administered by IV infusion over a minimum of 30 minutes. Detailed instructions for administration, including reconstitution and infusion rate, can be found in the pharmacy manual.

Donanemab is to be administered once Q4W. Donanemab must not be administered at a dosing interval of <21 days at any time in the study.

See Section 8.3.3.1 for infusion-related reactions.

For aducanumab, it is expected that the investigator review appropriate product label/institutional guidelines for confirmation dosing (i.e., need for pre-medication, dose, schedule, toxicity management and dose modifications).

Resuscitation equipment and rescue medications must be available wherever study intervention is administered.

6.2. Preparation, Handling, Storage, and Accountability

1. The investigator or designee must confirm appropriate storage conditions have been maintained during transit for all study intervention received and any discrepancies are reported and resolved before use of the study intervention.
2. Only participants enrolled in the study may receive study intervention. Only authorized study personnel may supply, prepare, or administer study intervention. All study

intervention must be stored in a secure, environmentally controlled, and monitored (manual or automated) area in accordance with the labeled storage conditions with access limited to the investigator and authorized study personnel.

3. The investigator or authorized study personnel are responsible for study intervention accountability, reconciliation, and record maintenance (i.e., receipt, reconciliation, and final disposition records).
4. Further guidance and information for the final disposition of unused study interventions are provided in the Pharmacy Manual.

6.3. Measures to Minimize Bias: Randomization and Blinding

This is an open-label study in which participants will be randomized in a 1:1 ratio to donanemab:aducanumab.

For between-group comparability, participant randomization will be stratified by amyloid burden and ApoE ϵ 4 status (noncarrier/heterozygous/homozygous). Any further stratification variables will be stated in the SAP. Assignment to treatment groups will be determined by a computer-generated random sequence using an IWRS. Randomization into 1 stratum may be discontinued or overenrolled at the discretion of the sponsor to manage between-group comparability.

All participants will be centrally assigned to randomized study intervention using an IWRS. Before the study is initiated, the log in information & directions for the IWRS will be provided to each site.

In order to maintain the scientific integrity of this trial, access to certain aspects of the study data will be strictly controlled prior to the potential interim analysis and testing of the primary and key secondary objectives. Access to the EDC system will be limited to those who require this information for their role and all access will be documented.

For the primary efficacy analysis database, that is, the database to which study statisticians (Lilly and/or its designee) have access, measurements from post-baseline florbetapir F18 PET scans will be scrambled or masked to preclude the ability to conduct the primary efficacy analysis. Scrambled or masked florbetapir F18 PET measurements will be used in the reporting database until the interim analysis or the 6-month database lock, and the same procedures will also be utilized for the testing of the objectives associated with 12- and 18-month outcomes.

In the event of an interim efficacy analysis assigned to the DMC, only the designated SAC, which is independent of the sponsor, will perform analyses on unblinded data, that is, the primary efficacy analysis database with correct treatment assignments.

Further details are included in the study blinding plan.

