4.1. General Considerations

Statistical analysis of this study will be the responsibility of the Sponsor or its designee.

Unless otherwise noted, tests of treatment effects will be conducted at a 2-sided alpha level of 0.05 (or equivalently, a 1-sided 0.025 alpha level); 2-sided CIs will be displayed with a 95% confidence level. If relevant, tests of interactions between treatment and other factors will be conducted at an alpha level of 0.05.

Participant assignment to treatment will be stratified by ApoE ϵ 4 genotype, and baseline amyloid level. These factors will be included in analysis models unless otherwise stated.

All amyloid plaque analyses will follow the ITT principle unless otherwise specified. An ITT analysis is an analysis of data by the groups to which participants are assigned by random allocation, even if the participant does not take the assigned treatment, does not receive the correct treatment, or otherwise does not follow the protocol.

When change from baseline is assessed, participants will be included in the analysis only if both a baseline and a postbaseline measure are available. Unless otherwise defined, a baseline measure is the last non-missing observation collected prior to the first administration of study medications. Endpoint is the last non-missing post-baseline measurement.

To allow for sequential testing, database locks and the testing of corresponding primary and key secondary objectives are expected to occur after all randomized participants have had a chance to complete the scheduled 24-week PET scan, the scheduled 52-week PET scan, and the scheduled 76-week PET scan. If an interim analysis occurs, a database lock will additionally occur after a sufficient number of participants (for example, approximately 75-125) have had a chance to complete the scheduled 24-week PET scan. Data collected during the immunogenicity and safety follow-up period will be summarized and analyzed separately.

Any change to the data analysis methods described in the protocol will require a protocol amendment only if it changes a principal feature of the protocol. Any other change to the data analysis methods described in the protocol, and the justification for making the change, will be described in the SAP and the clinical study report. Additional exploratory analyses of the data will be conducted as deemed appropriate.

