4.7.5. Safety MRIs

The frequency and percentage of participants with significant treatment-emergent MRI findings, especially Amyloid Related Imaging Abnormalities (ARIA) events such as vasogenic edema (ARIA-E) or microhemorrhage (ARIA-H) will be reported. Fisher's exact test will be used for treatment comparisons.

To evaluate white matter changes over time, a shift table will be created from the following categories:

- 0 = No lesions
- 1 = Focal lesions
- 2 = Beginning confluence of lesions
- 3 = Diffuse involvement of entire region

A listing of MRI data will also be presented.

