4.8.3. Subgroup analyses

To assess the effects of genetic factors and clinical severity of illness on treatment outcome, subgroup analyses for the primary endpoint, complete brain amyloid clearance, and mean changes in amyloid reduction will be conducted:

- Age - <65 , ≥ 65 .
- APOE4 Carrier Status – Carrier defined as E2/E4, E3/E4, or E4/E4 genotype; No-Carrier defined as all other genotypes
- Clinical staging at baseline – MCI (defined as $27 \leq \text{MMSE} \leq 30$) or mild AD (defined as $20 \leq \text{MMSE} \leq 26$)

The statistical models will be the same as those stated for the co-primary and key secondary objectives, with the addition of factors for the subgroup variable, the subgroup-by-treatment interaction, and the subgroup-by-visit interaction where appropriate.

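### ARIA is compared with a pooled Fisher's exact test, and no planned safety output shows it by the three ApoE levels used at randomization

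*Protocol*

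**What the plan says.** **Randomization.** Protocol 6.3: "For between-group comparability, participant randomization will be stratified by amyloid burden and ApoE" ε4 status, with the levels given in parentheses as noncarrier, heterozygous and homozygous. Protocol 8.6.1 makes ApoE genotyping mandatory, and SAP 4.3 summarizes genotype at baseline, so the three-level factor should be available for every randomized participant.

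**ARIA analysis.** SAP 4.7.5 plans frequencies and percentages of MRI findings, "especially Amyloid Related Imaging Abnormalities (ARIA) events such as vasogenic edema (ARIA-E) or microhemorrhage (ARIA-H) will be reported". On testing it says that Fisher's "exact test will be used for treatment comparisons". The only other ARIA output is a data listing: "A listing of MRI data will also be presented". No strata, covariates or ApoE breakdown are named.

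**Subgroups.** SAP 4.8.3 says that "subgroup analyses for the primary endpoint, complete brain amyloid clearance, and mean changes in amyloid reduction will be conducted". ApoE appears there as carrier versus non-carrier, and no safety outcome is included.

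**General rule.** SAP 4.1 says of the stratification factors: "These factors will be included in analysis models unless otherwise stated".

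**Elsewhere.** Protocol 8.3.4 lists ARIA-E and ARIA-H among the adverse events of special interest and refers their analysis to the SAP. Protocol 9.3.5 does the same for safety in general. No other section fills the gap.

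**The concern.** Comparing the safety of the two drugs, with ARIA on MRI named, is one of the trial's secondary objectives. If ARIA risk differs by ApoE level, a pooled two-by-two table has two weaknesses.

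- **Power.** The test ignores a factor that the randomization has balanced, so its reference variance is too large. Fisher's test is also conservative in its own right. A real difference between the drugs is then less likely to reach significance.
- **Location.** The pooled table cannot show whether a difference sits in one ApoE level, or whether differences in two levels cancel. Protocol 6.3 also lets the sponsor stop or over-enroll a stratum, so under an ApoE gradient the pooled ARIA percentages depend partly on the enrollment mix. Percentages within a level do not.

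**Working it through.** **The plan's own figure.** The only stated power is at least 98%, for 6-month amyloid clearance. It reproduces. With 45 per arm in the intermediate tau set (half of 90) and rates of 35.7% and 3.0%, the normal approximation is Φ[(|p1 − p2|√n − 1.96√(2p̄q̄)) / √(p1q1 + p2q2)] = Φ[(2.194 − 1.095)/0.509] = Φ(2.16) = 98.5%. It says nothing about ARIA, for which no power is stated.

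**Inputs**
- From the documents: about 200 participants randomized 1:1, so about 100 per arm if all are exposed; two-sided 0.05; three ApoE levels.
- Assumed, because the documents give none: ApoE shares 30/50/20% (30, 50 and 20 per arm), a common odds ratio of 2, and three ARIA risk patterns in the lower-risk arm. The higher-risk arm follows from p1 = 2·p0/(1 + p0).

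| ARIA risk by ApoE level, lower arm | Overall, lower arm | Overall, higher arm |
|---|---|---|
| 10/20/40% | 3 + 10 + 8 = 21.0% | 5.5 + 16.7 + 11.4 = 33.5% |
| 5/20/50% | 1.5 + 10 + 10 = 21.5% | 2.9 + 16.7 + 13.3 = 32.9% |
| 20/20/20% | 20.0% | 33.3% |

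**Tests compared.** With a_k events in one arm, m_k events in both arms and n_k participants per arm in level k:
- pooled Fisher's exact test (the SAP's choice);
- pooled score test, z = (a − b)/√(2N·p̄(1 − p̄)), where a and b are the total events in the two arms and N = 100;
- CMH, [Σ(a_k − m_k/2)]² / Σ[n_k²·m_k(2n_k − m_k) / ((2n_k)²(2n_k − 1))];
- the exact conditional version of the stratified test.

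**Simulated power**

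| ARIA pattern | Fisher | Pooled score | CMH by ApoE | Exact stratified |
|---|---|---|---|---|
| 10/20/40% | 46% | 52% | 55% | 49% |
| 5/20/50% | 36% | 42% | 50% | 43% |
| flat 20% | 52% | 58% | 58% | 52% |

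Independent repeats agree to within about 1.5 points. With no drug difference, Fisher rejects in about 2 to 3.4% of trials and CMH in about 4.4 to 5%, so CMH's gain does not come from exceeding the nominal level.

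**Splitting the gain.** Two steps separate Fisher from CMH.
- Fisher to pooled score (no longer an exact conditional test): 52 − 46 = 6, 42 − 36 = 6 and 58 − 52 = 6 points.
- Pooled score to CMH (using ApoE): 55 − 52 = 3, 50 − 42 = 8 and 58 − 58 = 0 points. The 8 reflects rounding and simulation error: a repeat with 60,000 trials gave 43.3% and 50.6%, a difference of 7.3.
- Exact against exact gives the same answer: 49 − 46 = 3, 43 − 36 = 7 and 52 − 52 = 0 points.

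**Why stratifying gains what it does.** The pooled test uses the variance p̄(1 − p̄); the stratified test uses the average within-level variance. At the lower arm's rates:
- 10/20/40%: 0.3×0.09 + 0.5×0.16 + 0.2×0.24 = 0.155, against 0.21×0.79 = 0.166 (ratio 0.93).
- 5/20/50%: 0.3×0.0475 + 0.5×0.16 + 0.2×0.25 = 0.144, against 0.215×0.785 = 0.169 (ratio 0.85).
- Flat: 0.16 against 0.16 (ratio 1).

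**What a pooled table can miss.** These cases are also assumed.
- Difference in homozygotes only (60% against 20%, 20 per arm; the other levels equal at 10% and 25%): pooled Fisher has 21% power, CMH 28%, and Fisher within homozygotes 65%.
- Opposite directions (20/25/35% against 10/25/50%): 6 + 12.5 + 7 = 25.5% and 3 + 12.5 + 10 = 25.5%. The pooled percentages are identical. CMH does not detect this pattern either (it rejects in 4.8%); only the by-level table shows it.

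**The case against.** The strongest reply has four parts.

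1. **Most of the power gap is not about ApoE.** This stands for the moderate and flat patterns, and for nearly half the gap in the steep one. A reader might infer from 46% against 55% that ignoring ApoE costs 9 points; about 3 of them are due to ApoE. If sparse cells force the exact stratified test, the gain over Fisher is only about 3, 7 and 0 points.

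2. **No rule is broken.** A reader might infer that SAP 4.7.5 contradicts SAP 4.1. It does not. The rule in 4.1 concerns models and allows exceptions, Fisher's test is not a model, and 4.7.5 names it expressly. Unadjusted Fisher tests are also the SAP's usual choice for adverse events, laboratory abnormalities and C-SSRS outcomes.

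3. **The documents do not say that ARIA risk depends on ApoE.** This stands. Protocol 7.1.3 calls ARIA an expected event on both drugs without mentioning genotype. The same argument for stratifying could be made for amyloid burden, the other stratification factor, although the documents do not give its levels. Every power figure above is therefore conditional.

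4. **Little hangs on the ARIA p-value.** It is ungated and unpowered, and the overall frequencies are reported in any case, so a reader should not infer that an overall excess would be concealed. Even CMH reaches only 50 to 58% here, so a non-significant result would be weak evidence under either test.

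The reply does not supply the by-level display. SAP 4.1 allows further exploratory analyses, and the listing would let someone build the table later. But a genotype split chosen after the data are seen, in an open-label head-to-head trial, carries less weight than one fixed in advance.

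**Conclusion.** The point holds as a modest, inexpensive improvement. The trial randomizes within three ApoE levels and requires the genotype, yet plans no safety output that uses those levels.

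The missing by-level table is the stronger half, because neither test can show where a difference lies. The change of test is the weaker half. Under 100 per arm, ApoE shares of 30/50/20% and a common odds ratio of 2, it raises power by about 9, 14 and 6 points across the three assumed ARIA patterns, of which about 3, 7 and 0 points are due to stratifying. If ARIA risk does not vary with ApoE, stratifying gains nothing and, in these simulations, costs nothing. The documents cannot settle which pattern applies.

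**What to change.** In SAP 4.7.5:
- Compare ARIA-E and ARIA-H between arms with a CMH test stratified by the three-level ApoE factor used at randomization, or with the exact stratified version if cells are sparse. State the sparseness rule in advance.
- Report a Mantel-Haenszel risk difference with its 95% CI for each.
- Tabulate ARIA-E and ARIA-H by arm within noncarrier, heterozygous and homozygous participants, and label the table descriptive.

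The cost is a few lines of SAP text and one extra table. No new data, visits or alpha are involved. The main limit is that homozygous cells will be small (20 per arm under the assumed share), so those rows describe and do not test.
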